#### PROGRAMMING:

- 1) Ask all respondents
- 2) Question to be asked of all responders. Subsequent survey questions are to be asked based on the type of healthcare provider the responder identifies as. Responders selecting response option "c" to be asked specific questions for "nurses" and "all responders". Responders selecting response option "d", "e", or "f" to be asked specific questions for "pharmacists" and "all responders".

You have qualified for our study, and we'd like to invite you to participate in our survey.

The survey will require about 15 minutes to complete. We ask for your undivided attention as you **complete the survey in one sitting**.

If you do not have 15 minutes right now, please click "stop," and return any time during the next 24 hours when you have an uninterrupted 15 minutes.

Again, please note that your responses will remain confidential, and will be reported only in the aggregate.

From time to time, surveys are conducted to evaluate the effectiveness of pharmaceutical company communications. The goal of this particular survey is to gauge healthcare providers' knowledge and current understanding of the labeling for BLINCYTO® (blinatumomab). Please note that this particular survey pertains to all indications in the labeling for BLINCYTO® (blinatumomab).

We want to emphasize that this is not a "test" of HCPs; rather, it is an attempt to assess pharmaceutical company educational activities.

Abbreviated Protocol: 20210065

Date: 22 March 2021 Page 17 of 37

Please read each question carefully and select the answer that you feel is most accurate, based only on your current knowledge and understanding of the educational materials you have reviewed. We want to inform you that you should not look-up online or other outside information while taking the survey. You should answer the questions based on your memory of the labeling and pharmaceutical company communications for BLINCYTO® (blinatumomab).

Note that your participation in this survey will NOT affect your ability to prescribe BLINCYTO® (blinatumomab).

For some of the survey questions, images are provided to give you a visual example of the document that we are referring to in the question. The writing in the image is intentionally blurred because we would like you to answer questions about the documents from memory.

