## Survey Methodology

Healthcare providers will be initially invited to participate in the survey by email (recruitment material, Appendix B). Majority of the surveys will be administered online and supplemented with telephone surveys. For those HCPs that opt for responding by telephone, the survey will be administered using computer-assisted telephone interviewing (CATI). In addition, direct mail invitations to participate in the online survey and/or hard copy surveys will be used to reach our target of completed surveys.

Screening questions will be placed at the beginning of the survey in order to determine whether HCPs are eligible to take part in a study. HCPs deemed ineligible by these questions are then terminated from the survey.

All possible answers for each survey question (not including screening questions) will be randomized. Participants will not be allowed to return to questions or be allowed to skip ahead during the survey administration. The correct answer choices will be provided on a screen at the end of the online survey. If the survey is completed by telephone, the correct answer choices will be provided by mail.

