## Appendix A. Questionnaire

## Screening questions:

Have you personally prepared, dispensed, and/or administered BLINCYTO
therapy to patients outside of the clinical trial setting in the last 12 months?
(Select all that apply)

a. I have personally prepared BLINCYTO therapy outside the clinical trial setting	0	
b. I have personally dispensed BLINCYTO therapy outside the clinical trial setting	0	
c. I have personally administered BLINCYTO therapy outside the clinical trial setting	0	
d. None of the above	0	TERMINATE

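### The 24-hour pause comes after the screener has named BLINCYTO and before the scored items, and the explicit look-up ban does not cover it

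*Protocol*

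**What the plan says.** **Screener (Protocol, Appendix A, Screening questions).** Question 1 begins "Have you personally prepared, dispensed, and/or administered BLINCYTO", and its first response option is "I have personally prepared BLINCYTO therapy outside the clinical trial setting". Questions 1a and 1b ask for numbers of infusions and patients. Every respondent therefore knows the product well before eligibility is settled at Question 5.

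**Qualifying text after Question 5.** In the order printed, it:
- asks respondents to "complete the survey in one sitting", which should take about 15 minutes;
- lets those without the time stop and "return any time during the next 24 hours when you have an" undisturbed period of that length;
- states the aim: "The goal of this particular survey is to gauge healthcare providers' knowledge and current understanding of the labeling for BLINCYTO";
- asks for answers that rest on present knowledge, and says "you should not look-up online or other outside information while taking the survey";
- adds "You should answer the questions based on your memory of the labeling" and the company's communications.

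**Scored items.** Question 7 (nurses) or 8 (pharmacists), with Questions 10 and 11, follow this text. Questions 7 and 8 ask what the prescribing information says.

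**Navigation (Survey Methodology).** "Participants will not be allowed to return to questions or be allowed to skip ahead during the survey administration".

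**Scoring (Descriptive Analyses).** A respondent with at least 75% of items correct counts as having knowledge. The proportion with knowledge is compared with 80% for each type of provider.

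**The concern.** The main endpoint is meant to capture what pharmacists and nurses know unaided, and the protocol takes trouble over this: answers from memory, blurred document images, no going back. The pause sits ahead of those controls. A respondent who takes it already knows which product the survey is about, has up to a day, and is under an explicit look-up ban that is worded for the time of taking the survey.

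Someone who reads the insert in that interval and then passes is scored the same as someone who knew the material beforehand. The error can only favour meeting the 80% threshold, and the planned confidence interval does not reflect it. The Background explains that this survey follows lower understanding of preparation and administration errors among these two groups at the 5-year assessment, so a flattering estimate would bear on the survey's main question.

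**Working it through.** **1. What a pausing respondent has seen.** Following the printed order: product named (Questions 1 to 1b), eligibility settled (Question 5), pause offered, aim stated, look-up ban and memory instruction given, scored items shown. At the pause offer the product is known and no scored item has been seen. The aim has been seen only if the goal statement is on the same screen, and the protocol does not show screen breaks.

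**2. Scope of the ban.** The explicit ban is tied to the time of taking the survey. The memory and one-sitting instructions point the same way in spirit, but neither says what may be done between stopping and returning.

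**3. The plan's own figures.** Table 1 under Sample Size gives 95% half-widths. The formula 1.96 × √(p(1−p)/n) reproduces all ten cells:
- n = 100, p = 10% to 50%: 0.0588, 0.0784, 0.0898, 0.0960, 0.0980
- n = 200: 0.0416, 0.0554, 0.0635, 0.0679, 0.0693

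Nothing in that table is disputed. At p = 0.75 and n = 100 the same formula gives 0.0849.

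**4. Illustration of the bias.** Let p be the true proportion with knowledge, and g the share of the remaining respondents who pause, read the label and then pass. Assume that reading never turns a pass into a fail. The expected observed proportion is

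q = p + (1 − p) × g, so the bias is (1 − p) × g.

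The documents give neither p nor g; both are assumptions, with g run from 0 to 0.30. Brackets show the binomial probability that at least 80 of 100 are scored as having knowledge.

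| p | g = 0 | g = 0.05 | g = 0.10 | g = 0.20 | g = 0.30 |
|---|---|---|---|---|---|
| 0.70 | 0.700 (0.016) | 0.715 (0.035) | 0.730 (0.068) | 0.760 (0.208) | 0.790 (0.461) |
| 0.75 | 0.750 (0.149) | 0.7625 (0.225) | 0.775 (0.322) | 0.800 (0.559) | 0.825 (0.788) |
| 0.78 | 0.780 (0.366) | 0.791 (0.470) | 0.802 (0.579) | 0.824 (0.780) | 0.846 (0.917) |

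**5. Conversion needed to reach 80%.** g = (0.80 − p)/(1 − p):
- p = 0.70: 0.10/0.30 = 0.33
- p = 0.75: 0.05/0.25 = 0.20
- p = 0.78: 0.02/0.22 = 0.09

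**6. What such a g requires.** Among those who would otherwise fail, g is the share who pause × the share of pausers who read the label × the share of readers who then pass. If every reader passes, 20% pausing and half of them reading gives 0.2 × 0.5 = 0.10; g = 0.20 needs, for example, 0.4 × 0.5. If some readers still fail, g is smaller.

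**The case against.** The case for leaving the text alone is a fair one.

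- **The aim may not be known at the pause.** A reader might infer that respondents learn both product and purpose and then have a day to prepare. The documents do not support the second half: the stop offer is printed before the goal statement, and whether they share a screen is not stated. Only knowledge of the product is established.
- **No item is visible.** A pausing respondent could only read the label on speculation. The text tells respondents they are not being tested, and the Compensation table lists the same $65 for both groups with no link to score, so the incentive is weak.
- **The intent is clear.** The one-sitting request, the reliance on present knowledge and the appeal to memory all discourage preparation, and the pause is offered only to find uninterrupted time.
- **Other routes exist.** The invitation (Appendix B) was not available to me and may already name the product. Survey Methodology also allows hard-copy completion, where look-up is not controlled at all. No remote survey can enforce a closed-book rule.
- **The size is assumed.** No rate of pausing or reading is given anywhere in the document.

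All of this stands as a limit on how large the effect can be. None of it closes the gap: the product is known, the interval is offered, and the explicit ban does not reach it. A reader might also treat the absence of a flag for resumed sessions, or of an analysis without them, as an omission. It is not counted as one here, because such handling can properly be left to a statistical analysis plan.

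**Conclusion.** The point holds as a small weakness in a stated procedure. It is neither a contradiction nor a numerical error. As printed, respondents who know the product may take up to 24 hours before the scored items without an explicit instruction against reading the label in between. Any resulting bias is upward.

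Its size cannot be taken from the documents and is probably modest. At an assumed true 75%, g from 0.05 to 0.30 gives 1.3 to 7.5 points, against a half-width of about 8.5 points at n = 100. It would take g = 0.20 to lift 75% to the threshold. These figures show the direction and what would be needed to matter; they are not estimates. A reader might conclude that the pause defeats the closed-book design or that a result above 80% could not be believed. The text does not support either conclusion. The case for change rests on how little the change costs.

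**What to change.** 1. Move the offer to stop for lack of time ahead of Question 1, onto a page that names neither the product nor the purpose, so that screening and scored items normally run in one session.
2. Extend the no-look-up sentence to any break between starting and finishing, and repeat it when a respondent re-enters.
3. Optionally, log resumed sessions from the platform's time stamps and report the main proportion with and without them. The analysis can be specified in the statistical analysis plan, but the log must be in place before fielding.

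**Cost.** One block of text moved, one sentence added and, if wanted, one logged field. Some ineligible people will see the time request, and a few respondents interrupted after Question 1 may be lost. Question 1 has to name the product to establish eligibility, so anyone who breaks off after it still has the cue; the second change is aimed at them. If the invitation already names the product, the reordering gains less, while the wording change and the log keep their value.

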#### PROGRAMMING:

1) Ensure that question instructions are clearly visible to responders by using appropriate font size and bold font

Abbreviated Protocol: 20210065

Date: 22 March 2021 Page 18 of 37

## **Survey questions:**

## **Key Risk Message Questions**

7. According to the BLINCYTO Prescribing Information/Package Insert, please answer if the following statements are true or false. If you are not sure, please select "not sure."

	BLINCYTO Preparation and Administration	True	False	Not sure
L1	Preparation and administration errors have occurred with BLINCYTO treatment.  NOTE: We are not asking whether you have personally seen these issues at your facility.	0	0	0
L2	The recommended dose for BLINCYTO is based on patient body surface area (BSA) for patients who weigh less than 45 kg and is fixed (ie, not based on BSA) for patients who weigh greater than or equal to 45 kg.	0	0	0
L3	Medication errors such as underdosing and overdosing can occur if BLINCYTO is prepared or administered incorrectly.  NOTE: We are not asking whether you have personally seen these issues at your facility.	0	0	0
L4	When preparing BLINCYTO, you should follow the preparation instructions provided in the Full Prescribing Information.	0	0	0
L5	The BLINCYTO infusion line or intravenous catheter should not be flushed when changing infusion bags because it can result in excess dosage.	0	0	0
L6	The use of BLINCYTO prepared with benzyl alcohol preservative is recommended for use in adult and pediatric patients across all weight ranges.	0	0	0

## PROGRAMMING:

- 1) Ask NURSE respondents
- 2) Example Prescribing Information visual aid to be displayed on screen
- 3) Display rows L4 and L6 ONLY if Q1 answer includes "a"
- 4) Randomize order of rows

Abbreviated Protocol: 20210065

Date: 22 March 2021 Page 19 of 37

8. Based on the BLINCYTO Prescribing Information/Package Insert, please answer if the following statements are true or false. If you are not sure, please select "not sure."

	BLINCYTO Preparation and Administration	True	False	Not sure
L1	Preparation and administration errors have occurred with BLINCYTO treatment.	0	0	0
	NOTE: We are not asking whether you have personally seen these issues at your facility.			
L2	The recommended dose for BLINCYTO is based on patient body surface area (BSA) for patients who weigh less than 45 kg, and is fixed (ie, not based on BSA) for patients who weigh greater than or equal to 45 kg.	0	0	0
L3	Medication errors such as underdosing and overdosing can occur if BLINCYTO is prepared or administered incorrectly.  NOTE: We are not asking whether you have personally seen these issues at your facility.	0	0	0
L4	When preparing BLINCYTO, you should follow the preparation instructions provided in the Full Prescribing Information.	0	0	0
L5	Reconstitute BLINCYTO with IV Solution Stabilizer for Injection.	0	0	0

#### PROGRAMMING:

- 1) Ask PHARMACIST respondents
- 2) Example Prescribing Information visual aid to be displayed on screen
- 3) Randomize order of rows
- The Full Prescribing Information/Package Insert contains the most complete instructions on BLINCYTO preparation (including admixing) and administration to minimize medication errors (including underdose and overdose).

(Select one answer)

a. True	
b. False	
c. I am not sure	

#### PROGRAMMING:

1) Ask all respondents

Abbreviated Protocol: 20210065

Date: 22 March 2021 Page 20 of 37

11. Aseptic technique must be strictly observed when preparing or administering the BLINCYTO solution for infusion.

(Select one answer)

a. True
b. False
c. I am not sure

## PROGRAMMING:

## 1) Ask all respondents

12a. Which of the following are true of your workplacesetting:

(Select all that apply)

a. Step-by-step instructions for preparing BLINCYTO are kept open for reference when BLINCYTO is prepared	
b. Preparation instructions were developed by our facility based on prescribing information/package insert	
c. Prescribing information/package insert is kept open for reference when BLINCYTO is prepared	
d. Preparation of BLINCYTO is checked by two pharmacists	
e. Proper dosing calculations for BLINCYTO are programmed into my facility's EMR	

## PROGRAMMING:

- 1) Ask all PHARMACIST respondents
- 2) Randomize order of rows

Abbreviated Protocol: 20210065

Date: 22 March 2021 Page 21 of 37

13a.	Which of the	following	are true of	vour workr	nlace setting.
ısa.	WILLIAM OF THE	IOIIOWIIIQ	are true or	voui worki	nace sellina.

(Select all that apply)

a. Tubing is primed by pharmacy staff before BLINCYTO is delivered for administration	
b. Dose on bag is checked by two nurses before BLINCYTO is administered	
c. Check-list for proper BLINCYTO administration is delivered, on paper, along with drug	
d. Check-list for proper BLINCYTO administration is kept on floor with similar information about other oncolytic agents	
e. Check-list for proper BLINCTYO administration is part of EMR	

#### PROGRAMMING:

- 1) Ask all NURSE respondents
- 2) Randomize order of rows

## **HCPs awareness and utilization of BLINCYTO REMS materials**

15. Prior to today, were you aware of the BLINCYTO REMS Website (www.blincytorems.com)?

(Select one answer)

a. Yes	
b. No	

### PROGRAMMING:

- 1) Ask all respondents
- 2) If "Yes," proceed to Question 16; if "No," skip to Question 18
- 16. Prior to today, have you accessed the BLINCYTO REMS website?

(Select one answer)

a. Yes	
b. No	

#### PROGRAMMING:

- 1) Ask if Q15 is "Yes"
- 2) If "No," proceed to Question 17a; if "Yes," skip to Question 17b

**Abbreviated Protocol: 20210065** 

Date: 22 March 2021 Page 22 of 37

17a. Why have you not accessed the BLINCYTO REMS website?

(Select all that apply)

- a. I have all the product information I need (eg, Full Prescribing Information/Package Insert) without referring to the website
- b. I prefer to obtain information from other sources (eg, Lexicomp, colleagues, sales representatives, societies)
- c. I do not have time in my workplace to access websites

#### PROGRAMMING:

- 1) Ask if Q16 is "No"
- 17b. How familiar are you with the content of the BLINCYTO REMS website?

(Select one answer)

- a. Very familiar
- b. Somewhat familiar
- c. Not very familiar

#### PROGRAMMING:

1) Ask if Q16 is "Yes"

Abbreviated Protocol: 20210065

Date: 22 March 2021 Page 23 of 37

18. From what sources have you learned about the risk of preparation and administration errors associated with the use of BLINCYTO? Select all that apply.

(Select one answer in each row)

Source	Yes	No
Full Prescribing Information/Package Insert		
BLINCYTO REMS Fact Sheet		
BLINCYTO REMS Website		
BLINCYTO promotional materials		
BLINCYTO product website		
Sales representatives from the manufacturer		
Medical science liaisons from the manufacturer		
Other healthcare professionals/colleagues		
BLINCYTO REMS communications (email, letters)		
Press Releases		
Professional Societies (eg, Oncology Nursing Society [ONS], American Society of Clinical Oncology [ASCO])		
Drug and prescribing information databases (eg, Physician's Desk Reference, Epocrates, Micromedex, Lexi-comp, others)		
Other (please specify:)		

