will also be calculated. Responses for questions related to preparation instructions and access to checklists and Product Information/Package Insert (PI) in the workplace setting and knowledge of indication for BLINCYTO will be described with proportions and 95% CIs for each response option. Similarly, proportions and 95% CIs will be reported for the awareness and use of the REMS materials (responses for Questions 15 to 32 in Appendix A).

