## PROGRAMMING:

- 1) Ask all respondents
- 2) Randomize rows
- 3) Free text field for the "Other" response option is a force response

Abbreviated Protocol: 20210065

Date: 22 March 2021 Page 24 of 37

19. Prior to today, were you aware of the **BLINCYTO REMS Letter or email for Healthcare Providers?** 

(Select one answer)

a. Yes
b. No
c. I am not sure

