#### PROGRAMMING:

- 1) Ask if Q26 is "Yes"
- 2) Example BLINCYTO REMS Letter or email for Hospital and Home Healthcare Pharmacists visual aid to be provided on screen
- 28. Prior to today, were you aware of the **BLINCYTO REMS Fact Sheet**?

(Select one answer)

a. Yes	
b. No	
c. Lam not sure	

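### Question 18 carries two incompatible answer instructions, so a blank row may mean No or missing, and its REMS website row is shown to respondents already recorded as unaware of the site or as never having opened it

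*Protocol*

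**What the plan says.** Question 18 in Appendix A is worded "From what sources have you learned about the risk of preparation and administration errors associated with the use of BLINCYTO? Select all that apply". The line directly beneath reads "Select one answer in each row", and the response area is a grid of sources with a Yes and a No column. Its programming note says "Ask all respondents", randomizes the rows, and marks only the free-text field of the Other row as a forced response. One row is the REMS website.

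The website has its own questions just before this. The routing note for Question 15 (awareness) is "If 'Yes,' proceed to Question 16; if 'No,' skip to Question 18". Question 16 (access) is restricted by "Ask if Q15 is 'Yes". A No at Question 16 leads to Question 17a, on reasons for not accessing the site, and then to Question 18.

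Survey Methodology (Section 3) expects most surveys to be completed online, supplements them with telephone interviews, and allows hard-copy surveys to reach the target. Respondents may neither return to earlier questions nor skip ahead. For Questions 15 to 32, Descriptive Analyses states that "proportions and 95% CIs will be reported for the awareness and use of the REMS materials".

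**The concern.** The two instructions give a blank row different meanings. In a tick-what-applies list, an empty row is a No. In a row-by-row grid, it is an unanswered item. The protocol does not say which applies, yet it plans a proportion and a confidence interval from the item, and the denominator depends on the answer. An analysis rule written later can fix a convention, but it cannot recover which instruction a respondent followed.

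The routing raises a second, separate problem. The same person can be on record as not knowing the website, or as never having opened it, and also as having learned from it about preparation and administration errors. Online and by telephone, the ban on going back means the earlier answer cannot be corrected.

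At stake are secondary results on how the REMS materials reach pharmacists and nurses: ambiguous source proportions, and website figures that can contradict each other within one report.

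**Working it through.** **1. The plan's own precision.** Table 1 under Sample Size uses the half-width 1.96 × √(p(1 − p)/n). At n = 100 and p = 0.20 this is 1.96 × √(0.20 × 0.80/100) = 0.0784, printed as 0.078. All ten cells reproduce to three decimals. No stated figure is in dispute; the half-width serves as a yardstick.

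**2. Where blank rows can arise.**
- Telephone: an interviewer can obtain an answer for every row.
- Online: the ban on skipping ahead may force each row, but the programming note for Question 18 forces only the Other text field.
- Paper: nothing can be forced, and the respondent reads both instructions.

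**3. Effect on a proportion.** Let p be the true Yes share and b the share of No rows left blank. If blanks are dropped, the reported share is p / [p + (1 − p)(1 − b)]. The protocol gives neither value; p = 0.20 and b = 0.25 to 0.50 are assumptions.
- b = 0.25: 0.20 / (0.20 + 0.80 × 0.75) = 0.20/0.80 = 25%, on 80 answered rows of 100.
- b = 0.50: 0.20 / (0.20 + 0.80 × 0.50) = 0.20/0.60 = 33%, on 60 answered rows of 100.

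The shift is 5 to 13 points, against a planned half-width of 7.8 points. Here b is the blank share across all modes. If only paper forms can have blanks, b = 0.50 would need about half of the No respondents to be on paper, which sits badly with a mostly online survey. The upper end is therefore realistic only if the online program also accepts blank rows.

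The error can also run the other way. If a quarter to half of respondents skip the row whatever their true answer, and blanks are counted as No, the reported share is 0.20 × 0.75 = 15% down to 0.20 × 0.50 = 10%.

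**4. Website routing, traced.**
- Question 15 No: goes directly to Question 18 and sees the website row.
- Question 15 Yes, Question 16 No: Question 17a, then Question 18, and sees the website row.
- Question 15 Yes, Question 16 Yes: Question 17b, then Question 18, and sees the website row.

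Only the third path is consistent with a Yes in that row. Let u be the share on the first two paths and f the fraction of them who tick Yes. Contradictory records are then u × f of all respondents. Neither rate is in the protocol. Under assumed values, u = 0.50 with f = 0.05 to 0.20 gives 2.5% to 10%, and u = 0.70 gives 3.5% to 14%.

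**5. Other tools.** The awareness items for the healthcare provider letter (Question 19), the pharmacist letter (Question 25) and the Fact Sheet (Question 28) all come after Question 18. No one has been recorded as unaware of those tools when Question 18 appears, so the routing contradiction is confined to the website.

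**The case against.** The best defence is that the grid itself settles the matter: Yes and No columns imply one answer per row, and the select-all phrase is a stray remnant. In a select-all item an unticked option would ordinarily count as No, and nothing in the plan says blanks are dropped. The telephone-assisted pre-test also checks that questions are clearly understood, so it may well expose the conflict. This is fair as to likelihood. It still leaves two live instructions in the questionnaire and a mode, paper, in which either can be followed. The assumed blank rates are only illustrations.

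A reader might go further and infer that Question 18 is a second, competing definition of use for every REMS tool. The text does not support that. Question 18 asks where one particular risk was learned, while Questions 16, 20, 21, 26, 27, 29 and 30 ask about access and reading. Someone can read the Fact Sheet and still have learned this risk from a colleague. Descriptive Analyses groups Questions 15 to 32 together but builds no composite measure of use.

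A reader might also infer that awareness of the letters and the Fact Sheet is inflated because Question 18 names them before the items that begin "Prior to today, were you aware of the". Those later items name the tool themselves and display an example, so the added effect of an earlier mention is unknown. Survey Pre-testing already lists order effects for study. With about five respondents per group it cannot quantify such an effect, but that does not make a possible effect a demonstrated bias.

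**Conclusion.** Two limited defects stand. First, Question 18 has contradictory answer instructions, which leaves the meaning of a blank row, and so the denominator of every source proportion, undetermined wherever blanks can occur. Under the assumed rates, a true 20% could be reported as 25% to 33% with blanks dropped; the protocol supplies no rates, and the upper end needs blanks online as well as on paper. Second, the routing allows self-contradictory website records, with a frequency that the documents do not let one estimate.

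Both concern secondary, descriptive results. The main knowledge endpoint rests on Questions 7 or 8, 10 and 11, which come before Question 18. Neither a double definition of use across all tools nor a proven upward bias in awareness follows from the text.

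**What to change.** - Delete the select-all phrase from Question 18 and require one Yes or No in every row, enforced online and by telephone. On paper, print that single instruction, count blank rows as missing, and report their number.
- Show the website row only to respondents who answer Yes at both Question 15 and Question 16, and report it with all respondents as the denominator. Both questions offer only Yes and No, so the filter has no unsure category to resolve. On paper it becomes a printed skip instruction.
- Add the position of Question 18 relative to Questions 19, 25 and 28 to the order effects examined in the pre-test. No reordering is needed on present evidence: moving Question 18 to the end would place it after every tool has been named, which could cue its own REMS rows.

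The cost is one deleted phrase, one required-response setting and one display rule before fielding. The small downside is that the filter removes a consistency check, since contradictory website answers would no longer be seen online or by telephone.
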